Clinical study protocol

Project Name: Prospective, single arm, Phase II clinical study of selmetinib hydrogen sulfate capsules in patients with neurofibromatosis type I

Sponsor: Sun Yat-sen Memorial Hospital of Sun Yat-sen University

Version number: V2.0

Version date: 2024.04.17

Project leader: [name]

Scheme signature confirmation:

Compliance Statement

In accordance with the provisions of the Good Clinical Practice for Drug Clinical Trials and the Administrative Measures for Clinical Studies initiated by Medical Institutions (Trial) and the Declaration of Helsinki, we promise to carry out this study according to this protocol. The participants must be trained to conduct the study after the written approval of the Ethics Committee and the written informed consent of the subjects, and the protocol revision shall be re-approved again.

1. Protocol abstract (title, brief description of study, study object, outcome measures, study intervention*, Sample size, etc., in 300–500 words)

This study focused on patients with neurofibromatosis type I, currently lacking effective drug therapy and a high recurrence rate after surgical resection. Hydrosulfate sametinib capsule as a MEK inhibitor, through selective binding mitogen activated protein kinase (MEK) 1 / 2 protein, can block the regulation of key cells mitogen activated protein kinase / extracellular signal regulation kinase signaling pathway, can induce tumor shrinkage, for disease control, surgical radical resection, reduce postoperative recurrence, reduce complications. This study aims to provide hydrosulphate seletinib to patients with neurofibromatosis type I, observe the efficacy of drug treatment, change patients without surgical indications into indications for surgery, increase the proportion of surgical resection and reduce the recurrence rate. In this study, the objective response rate (ORR) as the main outcome measure, the range, duration of response (DOR), and progression-free survival (PFS) as secondary outcome measures to explore the use of surgical resection rate, reduction of surgical resection range and postoperative complications, tumor shrinkage effect, and the stability of efficacy.

2. Introduction (Rereferences should be noted in the introduction)
 - 2.1 Research theoretical basis / background (explain why clinical studies are conducted from the limitations of disease, standard of treatment and known treatment, and explain the findings and importance of preclinical, pharmacological and related studies)

Neurofibromatosis (NF) has been included in the list of rare diseases in many countries including China, 96% of which are NF 1 subtypes, and the clinical manifestations of NF 1 are diverse^[1], Involmultiple systems

and can cause serious complications such as airway obstruction, spinal cord compression and motor dysfunction^[2-4]. Pheoxiform neurofibromas (PN) occur in 30 to 50% of NF 1 patients^[5, 6], PN progress fast, accompanied by serious appearance defects, high disability, and the risk of deterioration^[7-10]. According to the 2023 edition of the multidisciplinary diagnosis and treatment of type I neurofibromatosis, patients with NF 1 are more likely to have a variety of benign and malignant tumors than the normal population, including pNF, CNF, MPNST and OPG. Attention should be paid to the early identification and monitoring of the above tumors. Neurofibromas with MPNST should have accelerated growth, pain and hard texture. At the same time, systemic evaluation should be carried out, and patients with no signs of distant metastasis should undergo early surgical treatment as far as possible, and patients with distant metastasis can choose radiotherapy, chemotherapy and targeted therapy.

Neurofibromatosis type I (neurofibromatosis type 1, NF 1) is an autosomal dominant disorder with 50% of patients with familial and 50% sporadic mutations. NF 1 gene encodes neurofibromin, downregulates the activity of Ras-Raf pathway and suppresses cell proliferation; deficiency in neurofibrosis causes excessive activation of RAS pathway and causes uncontrolled cell proliferation in NF 1 patients^[5]. At present stage, the operation is the most commonly used, the main treatment, and neurofibroma has the characteristics along the nerve root growth, it is difficult to solve all lesions through surgery, lesions composed of extensive nerve and vascular tissue and normal tissue, surgical resection difficult and bleeding, incomplete resection after recurrence as high as 50%.

As a MEK inhibitor, it blocks the mitogen-activated protein kinase / extracellular signal-regulated kinase signaling pathway by selectively binding to the mitogen-activated protein kinase (MEK) 1 / 2 proteins that regulate key cellular responses^[11-13], And then induce tumor shrinkage,

creating conditions for disease control, surgical resection, reducing postoperative recurrence and reducing complications. Based on the targeted therapy of selmetinib capsule, this study monitored the efficacy of the enrolled patients, so as to verify the effectiveness of selmetinib capsule for NF 1 therapy.

2.2 Risk / benefit evaluation

2.2.1 Known potential risks

The potential risks of this study are mainly the adverse reactions after the use of selmetinib hydrosulphate capsules, the hyperprogression of tumor treatment caused by the study protocol itself, and the risk of sudden accidents in the study.

2.2.2 Known potential benefits

The potential benefit of the subjects is the subjects to achieve partial tumor remission, delay progression, reduce recurrence, and improve function; Entering the clinical study can get more attention from researchers and manage the disease changes in time, which is beneficial to the treatment of the disease.

2.2.3 Potential risk and benefit evaluation

Smetinib Insulphate capsule is indicated for pediatric patients with neurofibromatosis type I (NF 1) aged 3 years and older with symptomatic, inoperable plexiform neurofibromas (PN). It was approved to list in China on April 28, 2023, and was included in the medical insurance directory on December 13, 2023. Several guidelines, consensus and diagnosis and treatment norms in China recommend selmetinib hydrohydrogen sulfate for the treatment of NF 1-PN. The most common toxicity of selmetinib sulphate capsules are grade 1 and 2 gastrointestinal symptoms (nausea, vomiting, or diarrhea), asymptomatic elevated creatine phosphokinase levels, acnes rash, and paronychia with good safety and tolerability. Therefore, this

clinical study protocol has a low risk of disease progression and serious adverse events on the treatment of NF 1^[14, 15]. At the same time, in the future studies, the investigators will pay more attention to the subjects' systemic condition and tumor treatment condition, and the subjects will also gain some clinical benefit in this study.

3. Study objective and endpoint (list presentation objective (specific issues to be addressed), corresponding to the outcome measures)

3.1 Purpose

3.1.1 Main Purpose

The primary objective of this study is to explore the objective response rate (ORR) of tumors in patients with neurofibromatosis type I (NF 1).

3.1.2 Secondary Purpose

The secondary objective of this study is to explore the improvement in surgical resectable range, duration of remission (DOR), progression-free survival (PFS) in patients with neurofibromatosis type I (NF 1) treated with selmeteitinib capsules.

3.1.3 Exploratory Purpose

The exploratory purpose of this study is to explore the long-term efficacy and stability of efficacy in patients with neurofibromatosis type I (NF 1) treated with selmeteitinib capsules.

3.2., study indicators

3.2.2 Secondary indicators and Definitions

Scope of surgical resection: on the premise of not damaging the important organs and neurological functions invaded by the tumor, the proportion of resection can be divided into total resection / near total resection (90% resection range), subtotal resection (90% resection range 50%), and partial resection (resection range <50%).

Duration of response (DOR): the time between the start of CR or PR and the first assessment of PD or death from any cause.

Progression-free survival (PFS): the time from the start of treatment in the trial to tumor progression or death from any cause (whichever occurs first).

3.2.3, safety indicators

The subject's vital signs, blood routine, liver function, blood biochemistry, urine routine, stool routine, coagulation function, left ventricular ejection fraction (LVEF), creatine phosphokinase, vitamin E, and bleeding risk.

4. study population

4.1 Inclusion criteria

- (1) Age ≥ 18 years old
- (2) According to the updated NF 1 diagnostic criteria of the National Institutes of Health (NIH) in 2021,
 - ① 6 or more CALMs: $d > 5$ mm before puberty or $d > 15$ mm after puberty;
 - ② 2 or more neurofibromas of any type or 1 plexiform neurofibroma;
 - ③ Plaques in the axillary or inguinal area;
 - ④ Optic glioma (OPG);

⑤ Slit lamp examination of 2 or more Lisch nodules, or optical coherence tomography (OCT) / imaging of two or more near infrared (NIR) abnormalities;

⑥ Characteristic bone lesions, such as sphenoid dysplasia and anterolateral curvature of the tibia;

⑦ Pathogenic heterozygous NF 1 variants with allelic variant scores of 50% in normal tissues (such as leukocytes);

Patients with no parental history and fulfilling 2 or more clinical characteristics could be diagnosed with NF 1

Parents with a history of 1 or more clinical features can be diagnosed with NF 1

(3) Before enrollment, a head and neck surgeon performed a pathological biopsy of the solid tumor to clarify the pathological diagnosis and exclude the malignant peripheral schwannoma (MPNST)

(4) At least one measurable tumor lesion according to the efficacy evaluation criteria of solid tumors RECIST 1.1

(5) The tumor infringes on the brain, spine and other important organs, with no indication for surgical resection

(6) The performance status of the Eastern Cooperative Oncology Group (Eastern Cooperative Oncology Group, ECOG) was 0-1

(7) Blood routine: white blood cell count (WBC) 3.010^9 / L; Absolute neutrophil count (ANC) 1.510^9 / L; Platelet (PLT) 10010^9 / L; hemoglobin level (HGB) 9.0 g/dL (no corresponding supportive care, such as transfusion and increased leukocytes within 7 days).

(8) Liver function: 2.5 times aspartate aminotransferase (AST) and alanine aminotransferase (ALT); albumin (ALB) 30 g / L.

(9) Renal function: serum creatinine 1.5 times ULN or creatinine clearance (CrCl) 50 mL/min (using the Cockcroft / Galt formula); urinary protein (UPRO) <(+ +), or 24-hour urinary protein <1.0 g.

- (10) Cardiac function: blood creatine phosphokinase 200U / L, left ventricular ejection fraction (LVEF) 50%;
- (11) Did not participate in other clinical trials within the previous 30 days;
- (12) Patients who voluntarily participate in the project and sign the informed consent form.

4.2 Exclusion criteria

- (1) The patient had abnormal blood index, abnormal liver and kidney heart function, and cannot tolerate the clinical study process after multidisciplinary consultation and evaluation
- (2) The patient has become a malignant peripheral nerve schwannoma (MPNST) or has other serious complications such as malignant tumors and heart disease, or has previously undergone anti-tumor therapy such as surgery, chemotherapy and radiotherapy
- (3) The whole clinical study cannot be completed due to personal, social and economic reasons
- (4) There are previously serious systemic system diseases and the disease cannot be cured or drug control
- (5) Patients who are present in pregnancy

4.3 Lifestyle considerations (lifestyle related restrictions: smoking, drinking, exercise, diet, etc., and what measures will be taken if the subject needs drugs, treatments or surgery prohibited in the protocol)

After entering the clinical study, the subject needs a light diet, food, tobacco, alcohol, and no strenuous exercise. If the subject needs the medication, treatment or surgery unrelated to the clinical study, the investigator needs to evaluate the cause of the need for the drug, treatment and surgical treatment is the cause of the study, additional treatment due to accident or other reasons, consider the influence of the treatment on the study, and suggest the subject to receive conventional

treatment after withdrawal and seal the subject data.

4.4 Screening failures (definition of screening failures and how to process screening failed subjects)

Screening failure refers to the recruitment of subjects who failed to meet the inclusion criteria or the exclusion criteria after multidisciplinary evaluation. The study will inform the multidisciplinary consultation and give the current best treatment advice.

4.5 Recruitment and retention strategy (how to recruit subjects (location, method, expected number of people.....); How to retain subjects (multiple contact information, incentive); such as involving vulnerable groups: reason + safeguard measures; if having compensation or incentive measures: object, quantity, form, time, etc.)

This study will take offline, combining online recruiting subjects, offline main location for sun Yat-sen memorial hospital oral and maxillofacial surgery, including but not limited to posters, leaflets, lectures and other forms to attract more subjects, each interested patients on-site registration, leave contact information and continue to one-on-one explanation. If the subject is in financial difficulties, the investigator team will assist the subject in providing assistance with the charity fund application to reduce the financial burden of the subject.

5. research design

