5.4 Definition of end of study (e. g. last subject completes last follow-up)

5.5 Statistical analysis

5.5.1 Sample size and calculation basis

The estimated sample size was based on the objective response rate. The study hypothesis is that selmetinib sulphate capsule has shrinkage effect on NF 1. The study parameters are set: $\alpha = 0.025$ (one side),

Power=90%. Based on the results of relevant study or pre-test, the objective response rate (ORR) is expected to reach 40%, 29 cases were calculated using PASS 15.0 software, and considering 10% shedding rate, 33 subjects should be included.

5.5. 2 Data analysis set (e. g. full analysis set, compliance protocol set, safety analysis set)

Statistical analysis will be performed using the SAS statistical software (V. 9.4, SAS Institute) Statistical analysis software for calculation, if no special instructions, the main indicators use one-sided test, control the first class error α is 0.025, the remaining indicators use two-sided test, one class error is $\alpha = 0.05$. To calculate confidence intervals, calculate two-sided 95% confidence intervals if not otherwise specified.

(1) Full analysis set (full analysis set, FAS): consisting of all subjects who received at least one drug / treatment and obtained efficacy assessment. This dataset was derived from all subjects after removing subjects in the least and reasonable way.

(2) Safety analysis set (safety analysis set, SS): a population treated at least once / once and having at least one safety evaluation data. In the safety analysis, all patients will be analyzed by the actual drug drug group.

(3) Compliance with the protocol set (per-protocol set, PPS): all concomitant medications that met the trial protocol and did not use the impact effectiveness evaluation, good medication compliance (between 80% and 120%), excluded subjects who had major protocol violations and were judged to have a significant impact on the results. All protocol deviations excluding subjects from the compliant protocol set will be described in detail in the Statistical Analysis Plan (SAP) and completed prior to data lock.

5.3 5 Statistical analysis plan

Data description of statistical analysis, analysis method of primary / secondary indicators / safety indicators, statistical school positive method, control of bias, stratification / subgroup / sensitivity analysis, etc

Demographic, and other baseline characteristics

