Based on the analysis of FAS set, the demographic data, medical history, vital signs and other baseline data were statistically described, where the measurement data (age, BMI, XX, etc.) gave mean, SD, minimum, maximum, median, and gave frequency and corresponding percentage for count data (gender, XXX, etc.).

Analysis of efficacy indicators

(1) Main efficacy indicators

Point estimates for the main evaluation index (ORR) and estimated two-sided 95% confidence intervals using the Clopper–Pearson exact probability method. If the lower limit of the 97.5% confidence interval was less than the ORR rate of the historical control, the efficacy was considered better than the historical control.

(2) Secondary efficacy indicators: analysis using FAS and PPS analysis sets. For survival metrics, the digit survival time and its two-sided 95% confidence intervals were calculated. For the rate of each index, point estimates were performed and two-sided 95% confidence intervals were estimated using the Clopper–Pearson exact probability method. For the continuity index, the mean and two-sided 95% confidence intervals were calculated based on the normal distribution method, otherwise the median and two-sided 95% confidence intervals were calculated based on the percentile method.

Safety index analysis

The SS set was used to provide a statistical description of the incidence of adverse events / serious adverse events and adverse reactions, and to list the details of the occurrence of each adverse event in each subject, including the type and severity of adverse events. Evaluation of laboratory indicators, vital signs, electrocardiogram and other safety related indicators, compare and evaluate the changes before and after treatment, and give a statistical description of the clinical evaluation (normal, abnormal without clinical significance, abnormal with clinical significance, not checked) before and after treatment.

Principles of handling missing / deletion / follow-up data

LOCF (last observation carried forward), that is, the main index data is not observed at the last time; the secondary indicators and safety indicators are not filled.

6. Research intervention*

6.1 Study intervention content (description of intervention content, implementation steps, dose and route of intervention drug, frequency of intervention, product of test group and control group, etc.)

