6.4 Concomitant therapy (permitted adjuvant medication, complementary / replacement therapy)

If the subject has hypertension, diabetes, coronary heart disease and other diseases that need long-term drug control, the investigator and the relevant specialist should evaluate the impact of the disease and the relevant study protocol and determine the dose and duration of adjuvant medication.

6.4.1 Rescue (drug, treatment methods, relevant records.....)

The life hazards during the implementation of the clinical study protocol should be implemented in accordance with the clinical rescue plan, such as cardiopulmonary resuscitation, emergency airway management,

emergency surgical treatment, relevant records during hospitalization should be recorded in the medical record system, after discharge should be recorded in the adverse event record form, and the investigator should analyze whether the rescue causes are related to the study and discuss and discuss synchronously in the rescue records.

7. Discontinuation of the study intervention / subject discontinuation and withdrawal*

7.1 Study Intervention discontinuation (reasons / criteria: such as how many adverse events occurred, length of study discontinuation, how data were collected during discontinuation and how to reactivate the study intervention, whether follow-up was continued during discontinuation)

If the Grade 5 adverse event of CTCAE 5.0 standard reaches 10% of the number of subjects, the study should be discontinued, and the drug safety of the study protocol should be discussed to determine whether to adjust the dose of drugs in the study protocol, continue the follow-up during the study suspension, and maintain the follow-up record of the original subject.

7.2 Subjects discontinuation / withdrawal from the study (possible reason for subject discontinuation; involving implantable device, discuss how to remove / replace, obtain alternative materials, later contact with the subject, etc.)

When the subject stops or withdraws from the study due to dissatisfaction with the treatment effect of the study plan or his own economic reasons, he should actively communicate with the subject, encourage the subject to actively treat and help them apply for public welfare funds to complete the treatment. If the subject clearly withdraws, the investigator can continue to complete the follow-up without the study intervention.

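### Section 4.3 tells the investigator to suggest withdrawal and seal a subject's data, 7.2 lets follow-up continue, and the effect on the ORR denominator is left open

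*Protocol*

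**What the plan says.** **Section 4.3 (lifestyle considerations).** The trigger is: "If the subject needs the medication, treatment or surgery unrelated to the clinical study, the investigator needs to evaluate the cause". The investigator is then to "consider the influence of the treatment on the study, and suggest the subject to receive conventional" "treatment after withdrawal and seal the subject data" (one sentence, split by a page break). Withdrawal is therefore a suggestion that follows an evaluation. Sealing is not explained there or anywhere else in the protocol.

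**Section 7.2 (discontinuation and withdrawal).** "If the subject clearly withdraws, the investigator can continue to complete the follow-up without the study intervention". The reasons named just before this are dissatisfaction with the effect and economic reasons.

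**Section 6.4 (concomitant therapy).** "If the subject has hypertension, diabetes, coronary heart disease and other diseases that need long-term drug control", the investigator and the relevant specialist evaluate the impact and "determine the dose and duration of adjuvant medication". Such subjects are managed inside the study.

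**Section 5.5.2 (analysis sets).** The FAS is defined as "consisting of all subjects who received at least one drug / treatment and obtained efficacy assessment".

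**Statistical analysis plan paragraph of section 5, missing data.** The rule for the primary index is "LOCF (last observation carried forward), that is, the main index data is not observed at the last time". Secondary and safety indicators are not filled.

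**The concern.** Sections 4.3 and 7.2 both deal with a subject who leaves study treatment. One closes the record and the other allows it to stay open. Two investigators could handle the same patient differently and each point to the protocol.

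This matters for the primary endpoint because the trial has one arm: the result is a proportion, and its denominator is settled after treatment has begun. If sealing means that data are no longer collected or used, the subjects counted depend on a post-treatment event. Section 4.3 itself asks whether the need for treatment came from the study, an accident or something else, so a link to how the patient is doing cannot be ruled out. Duration of response and PFS also need progression or death dates, which stopped follow-up cannot supply. A later SAP cannot recover images that were never taken.

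**Working it through.** **1. The passages side by side**

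| Question | 4.3 | 7.2 | 6.4 |
|---|---|---|---|
| Situation | needs treatment unrelated to the study | clearly withdraws | chronic disease needing long-term medication |
| Participation | withdrawal suggested after evaluation | study drug stopped | continues |
| Follow-up | not mentioned | may continue | within the study |
| Data | sealed (undefined) | not mentioned | not mentioned |

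The tension between 4.3 and 7.2 is the stronger one. With 6.4 it is weaker: the heading of 4.3 speaks of prohibited treatments, but its operative sentence covers any unrelated treatment, and the protocol shows no list of prohibited treatments to narrow it.

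**2. How sealing could reach the ORR**

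In the schedule under 5.2.1, imaging is ticked in the first, fifth, eighth and ninth of nine columns. The column headings are not readable in the text at hand. I take the first column as screening, because the biopsy and infection tests are ticked only there. Two cases follow if sealing ends data collection:

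- Closed out before the fifth column: there is no post-baseline image, hence no efficacy assessment, and the subject is outside the FAS.
- Closed out after it but before the cycle-6 image: the subject stays in the FAS and is scored by LOCF on the earlier image.

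The paragraph on the primary analysis names no analysis set. I assume the FAS.

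**3. The plan's own figure**

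Section 5.5.1 gives 29 evaluable subjects and 10% dropout: 29 / (1 − 0.10) = 32.2, rounded up to 33. This reproduces. The allowance is 33 − 29 = 4 subjects, which I use as the size of the illustration. The protocol does not forecast how many subjects 4.3 would affect.

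**4. Effect on the estimate**

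Assume 13 responders among 33 treated, close to the expected 40%. With k non-responders lost, ORR = 13 / (33 − k), with Clopper–Pearson 95% limits:

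| k | ORR | 95% CI |
|---|---|---|
| 0 | 13/33 = 39.4% | 22.9–57.9 |
| 1 | 13/32 = 40.6% | 23.7–59.4 |
| 3 | 13/30 = 43.3% | 25.5–62.6 |
| 4 | 13/29 = 44.8% | 26.4–64.3 |

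If the four lost are all responders, ORR = (13 − 4) / (33 − 4) = 9/29 = 31.0%. If loss is unrelated to response, the expected bias is zero.

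**5. Effect on the decision**

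The protocol states no historical ORR, so a benchmark p0 has to be assumed. I use 10% to 20%, and read success as a lower confidence limit above p0. At 15%, take a trial with 9 responders:

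- 9/33: lower limit 13.3%, fails.
- 9/30: lower limit 14.7%, fails.
- 9/29: lower limit 15.3%, passes.

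For the one-sided error, let r be the smallest count with P(X ≥ r | n = 33 − k, p0) ≤ 0.025. If the k subjects removed are always non-responders, the actual error is P(X ≥ r | n = 33, p0).

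| p0 | r at k = 0 to 3 | actual error | r at k = 4 | nominal error | actual error |
|---|---|---|---|---|---|
| 10% | 8 | 0.0141 | 7 | 0.0216 | 0.0417 |
| 15% | 10 | 0.0195 | 9 | 0.0223 | 0.0495 |
| 20% | 12 | 0.0216 | 11 | 0.0197 | 0.0508 |

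Up to three lost non-responders leave the error below 0.025. The fourth lowers the threshold by one and takes the error to between 0.042 and 0.051.

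**The case against.** A reader might infer that 4.3 removes patients selectively and inflates ORR. The documents do not support that as a statement of fact, for five reasons:

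- Withdrawal is suggested after evaluation, not imposed.
- The stated trigger is treatment unrelated to the study. Life-threatening events have their own record-keeping and relatedness assessment in 6.4.1.
- Sealing may mean only archiving or locking the record. Nothing says that sealed subjects leave an analysis set. The FAS text asks that removals be minimal and reasonable, and it is the per-protocol set that drops subjects whose other medication affects the efficacy evaluation.
- A subject with a post-baseline image stays in under the FAS and LOCF rules, and the safety set keeps anyone treated who has safety data.
- No count or response status is given for these subjects, so the direction of any bias is unknown.

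All of this stands, and so does the remark that 4.3 and 7.2 are not literal opposites: 7.2 is permissive, and 4.3 does not mention follow-up. The change from failure to success with nine responders is also a stacked case. It needs an assumed benchmark and four lost subjects, all of them non-responders and all outside the FAS.

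What the objection does not remove is the gap itself. Even if sealing only archives the record, 4.3 does not require imaging to go on after withdrawal and 7.2 makes follow-up optional. A subject closed out before the first post-baseline image then falls outside the FAS. Whether images are taken is a matter of study conduct, so it cannot be left to the SAP.

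**Conclusion.** The concern holds as an inconsistency with a conditional consequence. Sections 4.3, 6.4 and 7.2 must be reconciled on what happens to data and follow-up once a subject needs other treatment. If sealing ends data collection or use, and if those lost are mainly non-responders, ORR is overstated. Four such losses out of 33 add 44.8 − 39.4 = 5.4 percentage points at 13 responders, and can roughly double the one-sided error at the assumed benchmarks. With fewer losses, loss unrelated to response, or loss of responders, the effect is smaller, nil or reversed. The figures rest on an assumed responder count, an assumed number lost, an assumed benchmark and use of the FAS for the primary analysis. That these subjects will be removed, or that they will be non-responders, is not established by the documents.

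**What to change.** 1. In 4.3, remove the sealing instruction, or define it as archiving that excludes nothing from collection or analysis.
2. Reconcile 4.3 with 6.4 and 7.2. State that subjects who stop study drug or start other treatment continue the scheduled follow-up and imaging under 7.2 unless they withdraw consent, and that all their data are kept.
3. In 5.5.2 and the missing-data paragraph, count every treated subject in the primary ORR denominator. A subject without a cycle-6 assessment counts as a non-responder. For the primary endpoint this replaces both LOCF and the FAS exclusion for lack of an efficacy assessment.

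The cost is a few sentences and continued use of visits already in the schedule. ORR may come out slightly lower, partly because an early response followed by a missing cycle-6 image would no longer be carried forward. No position is taken on who should stop treatment or which concomitant treatment is allowed.
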